6.11. Efficacy Analyses

6.11.1. Primary Outcome and Methodology

The primary objective of this study (H1) is to test the hypothesis that LY900014 is noninferior to insulin lispro on glycemic control (NIM=0.4% for HbA1c) in patients with T2D, when administered as prandial insulin (0 to 2 minutes prior to the meal), in combination with basal insulin for 26 weeks. There will be 2 primary analysis methods, each tested at the full significance level of 0.05.

CCI [REDACTED], the primary analysis method will use the copy reference approach to impute missing data based on multiple imputations with a pattern mixture model. This analysis is for the ITT estimand that will include all data collected from randomization through Week 26, regardless of IP use. The reference will be all observed data from the randomized patients in the same treatment group who discontinue IP and complete the study without missing data. After imputation, the primary efficacy comparison will be based on the contrast between LY900014 and insulin lispro from an ANCOVA. The model for the change from baseline to the Week 26 HbA1c endpoint will include treatment and strata (pooled country, type of basal insulin, and number of prandial doses at study entry) as fixed effects and baseline HbA1c as a covariate.

If there are only a limited number of patients in the reference group as described above that leads to a failure in performing the proposed multiple imputation analysis such that the model cannot converge, or the number of records without missing data is less than the number of records with missing data, the missing HbA1c measurement at Week 26 will be imputed by the patient-level observed baseline value plus a noise, assuming a washout of any potential treatment effect (or “return to baseline”). The noise follows a normal distribution with the variability estimated from the “washout HbA1c data.” The “washout HbA1c data” will be derived by subtracting the corresponding treatment mean at Week 26 from individual non-missing HbA1c values at Week 26.

CCI [REDACTED], the primary efficacy comparison will be based on the contrast between LY900014 and insulin lispro at Week 26 (Visit 18) from the MMRM analysis of change from baseline in HbA1c including data collected from all randomized patients prior to permanent discontinuation of IP through Week 26 (efficacy estimand). The model for the analysis of the primary efficacy endpoint of change from baseline in HbA1c will include the fixed class effects of treatment, strata (pooled country, type of basal insulin, and number of prandial doses at study entry), visit, and treatment-by-visit interaction, as well as the continuous, fixed covariates of baseline value. An unstructured covariance structure will be used to model the within-patient errors. Significance tests will be based on LS means and Type III tests. If this analysis fails to converge, the following covariance structures will be tested in order:

- Toeplitz with heterogeneity
- autoregressive with heterogeneity
- compound symmetry with heterogeneous variances
- Toeplitz
- autoregressive
- compound symmetry without heterogeneous variances

The first covariance structure that converges will be used. The Kenward-Roger approximation will be used to estimate denominator degrees of freedom.

For both primary analysis approaches, LY900014 will be declared noninferior to insulin lispro if the upper limit of the 2-sided 95% CI for the LS mean difference in the change from baseline in HbA1c for LY900014 minus insulin lispro is below +0.4%. In addition, the 95% CI for the treatment difference will be compared to an alternative NIM of +0.3%. Both estimands will be tested at the full significance level of 0.05.

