7.8.2. Special Treatment Considerations

After discontinuation of IP at the end of the treatment period or earlier, randomized patients should restart the prandial insulin used prior to study entry or transition to a rapid-acting insulin analog other than insulin lispro if the patient was not treated with insulin lispro prestudy. Patients may continue treatment with the basal insulin used during the study or return to their prestudy basal insulin at investigator discretion.

Please also refer to [Appendix 8](#) for information regarding the insulin lispro antibody follow-up assessment. During this follow-up period, OAMs used during the study treatment period should be continued and other prestudy OAMs may be considered at investigator discretion as appropriate.

Investigators should provide patients with appropriate guidance for glucose monitoring and insulin dose adjustment throughout the follow-up period in order to maintain glycemic control.

8. Discontinuation Criteria

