10.3.3. Efficacy Analyses

10.3.3.1. Primary Analyses

The primary objective of this study is to test the hypothesis that LY900014 is noninferior to insulin lispro on glycemic control (NIM=0.4% for HbA1c) in patients with T2D, when administered as prandial insulin (0-2 minutes prior to the meal), in combination with basal insulin for 26 weeks. There will be 2 primary analysis methods, each tested at the full significance level of 0.05.

CCI, the primary analysis method will use the copy reference approach to impute missing data based on multiple imputations with a pattern mixture model. This analysis is for the ITT estimand (treatment regimen estimand) that will include all data collected from randomization through Week 26, regardless of IP use. The reference will be all observed data from the randomized patients in the same treatment group who discontinue IP and complete the study without missing data. After imputation, the primary efficacy comparison will be based on the contrast between LY900014 and insulin lispro from the ANCOVA analysis of change from baseline to Week 26 in HbA1c using all randomized patients as described in Section 10.3.1.

If there are only a limited number of patients in the reference group as described above that leads to a failure in performing the proposed multiple imputation analysis, the reference will be changed to include all observed data from all randomized patients in the same treatment arm who complete the study without missing data.

CCI, the primary efficacy comparison will be based on the contrast between LY900014 and insulin lispro at Week 26 (Visit 18) from the MMRM analysis of change from baseline in HbA1c including data collected from all randomized patients prior to permanent discontinuation of IP through Week 26 (efficacy estimand). The analysis model and selection of covariance structure is described in Section 10.3.1.

For both primary analysis approaches, LY900014 will be declared noninferior to insulin lispro if the upper limit of the 2-sided 95% CI for the LS mean difference in the change from baseline in HbA1c for LY900014 minus insulin lispro is below +0.4%. In addition, the 95% CI for the treatment difference will be compared to an alternative NIM of +0.3%. Both estimands will be tested at the full significance level of 0.05.

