Eligibility	Inclusion/Exclusion	Previous insulin therapy	Mixed (monitoring and clinical database)	CRF Prior Diabetes Therapies / Concomitant Therapy panel data to indicate not compliant with entry criteria #3, #32, #33. CCI [REDACTED]
Investigational Product	Treatment Assignment/ Randomization Error		Mixed (monitoring and clinical database)	IWRS data entry errors that impact patient stratification, for example, lab data indicated different strata from IWRS stratification report. Dispensing error: Patient is assigned to a treatment, but site gave a different treatment to the patient.
Investigational Product	Unblinding		Non Programmable (monitoring)	Any inadvertent unblinding affecting patients, investigator or sponsor.
Investigational Product	Patient Took Medication Not Fit for Use		Non Programmable (monitoring)	Study Drug not fit for use administered to patient.
Investigational Product	Other	Use of expired CT material	Non Programmable (monitoring)	CCI [REDACTED]

Description of Important Protocol Deviations

Category	Sub-categories	Description	Source	Methods of Identification
Study Procedures	Violation of Discontinuation Criteria		Mixed (monitoring and clinical database)	Patients not discontinued from treatment and/or study despite having met protocol specified discontinuation criteria. CCI [REDACTED] Protocol Section 8.
Study Procedures	Excluded Conmeds		Mixed (monitoring and clinical database)	CRF Prior Diabetes Therapies / Concomitant Therapy panel data to indicate not compliant with entry criteria #34 and study-specific restriction on concomitant therapies Table ITRN.8 in the study protocol. CCI [REDACTED]
Study Procedures	Lab/Imaging Criteria	Missing HbA1c at baseline/at the primary endpoint	Mixed (monitoring and clinical database)	Central laboratory data to indicate that a). HbA1c is not collected at both Visit 7 and Visit 8 or b). HbA1c is not collected at the primary endpoint (only applicable to patients who completed the primary endpoint without early discontinuation from the study).
Study Procedures	Visit Schedule Criteria		Programmable (clinical database)	CRF Subject Visit panel data to indicate that 2 consecutive office visits are completely missing.
Study Procedures	Other	Electronic Clinical Outcomes Assessment (eCOA)	Programmable (clinical database)	Comparison of patient data from CRF and eCOA to identify randomized patients who have no ed diary data entered.

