6.11.4. Sensitivity Analyses for Missing Data

A missing-not-at-random (MNAR)-based analysis will be performed for both the efficacy and ITT estimands to assess sensitivity to departures from the missing-at-random (MAR) assumption by repeatedly adjusting the imputations of missing data to provide a progressively more severe stress test (Ratitch et al. 2013). The basic idea is to impute the missing values and add a value (delta) to the imputed values of the experimental treatment group and perform an analysis for the primary endpoint on the delta-adjusted data set to see whether the conclusion of the primary analysis is overturned. If not, a larger delta is chosen and the process repeated until the primary result is overturned. If the delta required to overturn the primary result is not a plausible departure from MAR, then the primary result is robust to plausible departures from MAR. Imputation under the noninferiority null method (where delta equals the NIM) will be included as a special case of the progressive stress test.

For the ITT estimand, the reference group will be as described for the **CC1** primary analysis, and ANCOVA on the change from baseline to Week 26 in HbA1c will be used.

For the efficacy estimand, the reference group will be the insulin lispro treatment group. Imputation will be for all longitudinal visits.

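### Does the return-to-baseline fallback for missing Week 26 HbA1c make the ITT noninferiority test too lenient?

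*SAP*

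**What the plan says.** The ITT primary analysis imputes by copy reference, using same-arm patients who stopped study insulin but stayed to the end with complete data. SAP 6.11.1 gives two triggers for leaving that method: the model does not converge, or complete records are fewer than missing ones. The missing value is then "imputed by the patient-level observed baseline value plus a noise, assuming a washout of any potential treatment effect". The noise is normal, with its spread obtained by "subtracting the corresponding treatment mean at Week 26 from individual non-missing HbA1c values at Week 26". Noninferiority is declared when the upper 95% limit "for LY900014 minus insulin lispro is below +0.4"%, and the same interval is also compared with 0.3%.

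The fallback in Protocol 10.3.3.1 was different: "the reference will be changed to include all observed data from all randomized patients in the same treatment arm", restricted to those who complete without missing data. The SAP revision history (Section 3) records the replacement.

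SAP 6.11.4 plans a delta stress test for both estimands, with delta added to the imputed values of the experimental arm: "Imputation under the noninferiority null method (where delta equals the NIM) will be included as a special case of the progressive stress test". Its ITT sentence begins "For the ITT estimand, the reference group will be as described for the" and, after a redacted word, points to the primary analysis.

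On therapy after study insulin is stopped, Protocol 7.8.2 says "randomized patients should restart the prandial insulin used prior to study entry", or move to a rapid-acting analog other than lispro if they were not on lispro before the study.

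**The concern.** Imputation toward no difference is cautious for superiority but can be lenient for noninferiority. Here every imputed patient has an expected change of zero whichever arm they are in, so part of each arm is equal by construction, and the diluted estimate is the one compared with the margin. In the graphical scheme all alpha starts on H1, so a false H1 would also open the ITT tests of H2 to H4.

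Two wording points add to the doubt:

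- The ITT sentence in SAP 6.11.4 refers to a reference group, and return-to-baseline imputation has none.
- SAP 6.11.1 imputes the missing Week 26 value without restriction, while Table 6.2 mentions only patients who leave the study before Visit 18. Completers without a Week 26 HbA1c, a case listed in Table 6.3, could be read either way. Washout is least convincing for them and for patients who leave shortly before Week 26.

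**Working it through.** **Inputs from the documents.** Margin 0.4, SD 1.1, true difference 0, 284 completers per arm (SAP 5.2). 670 randomized and 568 completing (Protocol 5.2), so non-completion is 102/670 = 15.2%. One-sided error is 2.5%, from the upper limit of a two-sided 95% interval. The 15.2% is an upper value for missing HbA1c: patients off study insulin are encouraged to stay and give HbA1c (Protocol 8.1), and Table 6.2 requires at least one post-baseline value.

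**The plan's own figure.** 0.4 / (1.1 × √(2/284)) = 4.33, and Φ(4.33 − 1.96) = 99.1%. The stated power of at least 99% is reproduced.

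**Shrinkage.** With missing shares mT and mC and observed mean changes μT and μC, the expected fallback estimate is (1 − mT)μT − (1 − mC)μC. With equal m this is (1 − m) × the observed difference. The delta run adds mT × 0.4.

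**If the full 0.4 persists in imputed patients.** The normal approximation uses SE = 1.1 × √(2/335) = 0.085 and ignores the added noise. The simulation applies the SAP noise and Rubin's rules: 335 per arm, 20 imputations, 4,000 trials, data missing completely at random, control change −0.5, baseline SD 0.8, baseline to Week 26 correlation 0.4, and Week 26 SD set so that the SD of change is 1.1.

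| Missing share, both arms | 5% | 10% | 15.2% |
|---|---|---|---|
| Expected estimate, fallback | 0.380 | 0.360 | 0.339 |
| False noninferiority, normal approximation | 4.2% | 6.8% | 10.7% |
| False noninferiority, simulated | 3.2% | 4.5% | 6.7% |
| Expected estimate, fallback plus delta 0.4 | 0.400 | 0.400 | 0.400 |
| False noninferiority with delta 0.4, simulated | 1.8% | 1.4% | 0.9% |

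The noise widens the interval and takes back part of the dilution. Other assumed inputs that keep the SD of change at 1.1 give, at 15.2% missing:

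- 4.9% (baseline SD 0.7, correlation 0.6)
- 6.0% (both SDs 1.1, correlation 0.5)
- 7.6% (SDs 0.8 and 1.0, correlation 0.27)

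Values of 7.8% and 8.6% arise with SDs 0.8 and 1.0 and correlations 0.5 and 0.7. Those imply SDs of change of √(1.64 − 0.80) = 0.92 and √(1.64 − 1.12) = 0.72, not the SAP's 1.1.

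**If only part persists.** Let a fraction p of the on-treatment difference d persist in the missing patients. The ITT difference is d × (1 − m + pm) and the fallback estimates d × (1 − m). Fix the ITT difference at 0.4 with m = 0.152:

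- p = 1: d = 0.400, estimate 0.339.
- p = 0.5: d = 0.4/0.924 = 0.433, estimate 0.848 × 0.433 = 0.367. Simulated error is about 2 to 3.6% across the inputs tried.
- p = 0: d = 0.4/0.848 = 0.472, estimate 0.848 × 0.472 = 0.400. There is no shrinkage against the ITT target; only the extra noise remains. Simulated error is 0.5 to 1.8% over 5.1 to 15.2% missing.

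**Unequal missingness.** A separate term (mC − mT) × μC appears. With μC = −0.5 and a 5-point imbalance it is ±0.025. At mT 12.7% and mC 17.7% with a persisting 0.4, the estimate is 0.324 (simulated error 8.6%), and the delta run gives 0.375 (2.2%). The delta run restores the dilution but does not remove this term.

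**What tying the claim to the delta run would cost.** With no true difference, power at the 0.4 margin stays between 98.8% and 100.0%, depending on the set-up. At a true difference of 0.1 and 15.2% missing:

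- 98.7% to 91.0% (SDs 0.8 and 1.0, correlation 0.27)
- 99.5% to 95.6% (SDs 0.8 and 1.0, correlation 0.5)
- 98.7% to 89.6% (both SDs 1.1, correlation 0.5)

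The losses are 7.7, 3.9 and 9.1 points. False noninferiority would then be 0.5 to 1.8% with full persistence, and at most 1.1% with washout.

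**The case for a change.** The best case for acting is that the dilution is certain once the fallback runs, it favors the sponsor's claim, the corrective run is already planned, and a few sentences before unblinding would bind the two together. The protocol's same-arm fallback keeps the arm difference and held error at 2.2 to 2.7% in the same simulations when the difference persists. All of this is correct as arithmetic.

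It falls short because the inflation needs two things together: the fallback must be triggered, and most of a 0.4 difference must persist in people who have left the study. The documents give no probability for either. Under a treatment-regimen estimand, with both arms back on non-study prandial insulin, a difference near zero among dropouts may be the right target rather than a bias. Making a sensitivity run a co-requirement overcorrects even in the worst equal-missingness case, and because all alpha starts on H1 it also makes ITT H2 to H4 harder to reach. Statisticians can reasonably differ on that trade.

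The wording points stand as small gaps. Adding delta to return-to-baseline values in the LY900014 arm needs no reference group, and the general text of SAP 6.11.4 already describes that step. SAP 6.11.1, read plainly, covers any missing Week 26 value. Part of SAP 6.3 and a word in the 6.11.4 sentence are redacted, so clarifying text may exist there. Reporting the protocol's fallback alongside would be informative but would change no decision.

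**Conclusion.** No change is needed. The fallback shrinks the ITT estimate by at most about 0.06 HbA1c points at a true 0.4 with equal missingness, and by less at the missing shares that are likely. Its error is above nominal only if much of the arm difference survives in patients without Week 26 data, and below nominal if they wash out. The planned stress test shows how far the conclusion depends on that assumption, and the efficacy-estimand MMRM is untouched. For HbA1c superiority (H4) the shrinkage is conservative.

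This rests on assumed SDs, correlations and missing shares, on data missing completely at random, and, apart from the one imbalance check, on equal missingness. Strata were not simulated. The remaining gaps, how delta is applied under the fallback and whether completers without a Week 26 value are imputed, are ones an analyst would fill sensibly from SAP 6.11.1 and 6.11.4 as written.

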5.2. Number of Participants

Approximately 838 participants will be screened to achieve 670 randomized patients and 568 patients completing 26 weeks of treatment.

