8.1. Discontinuation from Study Treatment

In the event that the patient is discontinued from the study treatment, the investigator should encourage the patient to remain in the study for continued safety monitoring.

Lilly recognizes the importance of complete data collection. This study includes elements to minimize missing data. Randomized patients who are discontinued from IP before study completion are encouraged to remain in the study for continued monitoring. For patients who remain in the study after early discontinuation of IP, both efficacy (including HbA1c) and safety data will be collected at scheduled visits. The difference between stopping IP and discontinuing the study will be explained to patients as part of the informed consent, and patients will be encouraged to continue in the study even if they stop study drug. In addition, study site investigators will be trained on the importance of complete data collection, with additional re-education of sites and patients as necessary.

8.1.1. *Permanent Discontinuation from Study Treatment*

Patients will be discontinued from the IP in the following circumstances:

- The investigator may decide that the patient should stop IP. If this decision is made because of an AE, SAE, or a clinically significant laboratory value, the study drug is discontinued for that patient and appropriate measures are to be taken. Lilly or its designee is to be alerted.
- The patient may decide to stop IP.
- If the patient becomes pregnant.
- If an investigator, study site personnel performing assessments, or patient is unblinded, the patient must discontinue IP.
- If the patient, for any reason, requires treatment with another therapeutic regimen or therapeutic agent that has been demonstrated to be effective for treatment of the study indication. Discontinuation from IP should occur prior to introduction of the new agent.
- Use of prohibited concomitant medication, see [Table ITRN.8](#).
- If the patient has not taken IP for more than 14 consecutive days.

Discontinuation of the IP for abnormal liver tests **should be considered** by the investigator when a patient meets one of the following conditions after consultation with the Lilly designated medical monitor:

- ALT or AST >8X ULN.
- ALT or AST >5X ULN for more than 2 weeks.
- ALT or AST >3X ULN and TBL >2X ULN or prothrombin time >1.5X ULN.

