- replacing the imputation method with **CCI** “return to baseline” imputation method when the number of patients who discontinued IP but complete the study procedure without missing data is very limited
- updating the transition weights in the graphical testing scheme based on the results from Phase 1b studies (I8B-FW-ITRH and I8B-MC-ITRW)

- adding the on IP definition for mixed-meal tolerance test (MMTT) for which the 14-day rule is not applicable
- removing vital sign analyses except weight analysis for the lead-in period
- adding analysis details (for example, defining the pooled country used in the statistical modeling and region for subgroup analyses) and removing contradictory statements
- clarifying the analysis of important protocol deviations when duplicates occur

4. Study Objectives

Table 4.1 shows the objectives and endpoints of the study.

Table 4.1. Objectives and Endpoints

Objectives	Endpoints
Primary Objective	
1. (H1) To test the hypothesis that LY900014 is noninferior to insulin lispro on glycemic control (NIM=0.4% for HbA1c) in patients with T2D, when administered as prandial insulin (0 to 2 minutes prior to the meal), in combination with basal insulin glargine or insulin degludec for 26 weeks	1. Difference between LY900014 and insulin lispro in change from baseline to Week 26 in HbA1c
Multiplicity Adjusted Objectives	
2. (H2) To test the hypothesis that LY900014 is superior to insulin lispro in controlling 1-hour PPG excursions, when administered as prandial insulin	2. Difference between LY900014 and insulin lispro in the 1-hour PPG excursion (serum glucose measured 1 hour after the start of the meal minus fasting serum glucose) from an MMTT at Week 26
3. (H3) To test the hypothesis that LY900014 is superior to insulin lispro in controlling 2-hour PPG excursions when administered as prandial insulin	3. Difference between LY900014 and insulin lispro in the 2-hour PPG excursion (serum glucose measured 2 hours after the start of the meal minus fasting serum glucose) from an MMTT test at Week 26
4. (H4) To test the hypothesis that LY900014 is superior to insulin lispro on improving glycemic control (HbA1c) when administered as prandial insulin	4. Difference between LY900014 and insulin lispro in change from baseline to Week 26 in HbA1c
Other Secondary Objectives	

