5.2. Determination of Sample Size

Assuming a noninferiority margin (NIM) of 0.4%, no true difference between treatment arms, and a standard deviation (SD) of 1.1%, 568 completers (284 in each treatment group) will provide at least 99% power to show noninferiority between LY900014 and insulin lispro in change from baseline to 26 weeks in hemoglobin A1c (HbA1c) using the upper limit of a 2-sided 95% confidence interval (CI) (LY900014 – insulin lispro). **CCI**

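### Should the return-to-baseline fallback take its noise from the ANCOVA residual variance rather than the full Week 26 HbA1c variance?

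*SAP*

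**What the plan says.** SAP 6.11.1 gives two primary analyses of Week 26 HbA1c. For the ITT estimand, missing values are multiply imputed by a copy-reference approach. The result is then analysed by ANCOVA on treatment, three stratification factors and baseline HbA1c.

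The fallback applies if the imputation model cannot converge or if "the number of records without missing data is less than the number of records with missing data". SAP 3 describes the circumstance as arising "when the number of patients who discontinued IP but complete the study procedure without missing data is very limited". The missing value is then "imputed by the patient-level observed baseline value plus a noise, assuming a washout of any potential treatment effect". The noise is normal, and its variability comes from Week 26 data "derived by subtracting the corresponding treatment mean at Week 26 from individual non-missing HbA1c values at Week 26". Centring is therefore on the arm mean only, with no adjustment for baseline or strata.

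The only HbA1c SD in the documents is in the sample-size statement (SAP 5.2; Protocol 10.1): "a standard deviation (SD) of 1.1%, 568 completers (284 in each treatment group) will provide at least 99% power to show noninferiority". It is attached to change from baseline. Protocol 5.2 plans for "670 randomized patients and 568 patients completing 26 weeks of treatment". Under Protocol 8.1, for patients who "remain in the study after early discontinuation of IP, both efficacy (including HbA1c) and safety data will be collected at scheduled visits".

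**The concern.** Each imputed value already carries the patient's own baseline. Noise with the full between-patient variance of Week 26 HbA1c adds the baseline-predictable spread a second time. Against the ANCOVA residual variance, the noise variance is too large by the factor 1/(1 − ρ²), where ρ is the baseline-to-Week 26 correlation. That holds for any ρ other than zero.

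The result would be an unnecessarily wide interval in one of the two primary analyses. The same analysis tests HbA1c superiority (H4) and supplies the comparison with the +0.3% margin, so the apparent cost is precision for those two. The visible text gives no reason for choosing the full variance.

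**Working it through.** **Inputs from the documents.** SD 1.1; margins 0.4 and 0.3; 284 completers per arm; 670 randomized, so 335 per arm; planned non-completers 670 − 568 = 102, and 102/670 = 15.2%.

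**Assumed, because the documents do not give them.** Baseline SD 0.80; Week 26 SD 0.95 or 1.1; the planning 1.1 read as the SD of change; Rubin's rules; data missing completely at random. SAP 6.3, on missing data, is largely redacted, so the pooling rule and the number of imputations may be stated there.

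**The plan's own figure.** SE = 1.1 × √(2/284) = 0.0923. Power against 0.4 is Φ(0.4/0.0923 − 1.96) = 99.1%, which agrees with the stated 99%.

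**Implied correlation.** ρ = (s_b² + s_w² − 1.1²)/(2 s_b s_w).
- Week 26 SD 0.95: (0.64 + 0.9025 − 1.21)/1.52 = 0.22. Residual SD = 0.95 × √(1 − 0.22²) = 0.927.
- Week 26 SD 1.1: (0.64 + 1.21 − 1.21)/1.76 = 0.36. Residual SD = 1.025.

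**Approximate standard error.** With missing share m, residual variance s_r² and noise variance s_n², the total variance is about (2/335) × [(1 − m)s_r² + 2m s_n²]. One m s_n² comes from within imputations and one from between.

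| Week 26 SD | SAP noise | Residual noise | SD-of-change noise | SAP vs residual | SAP vs change |
|---|---|---|---|---|---|
| 0.95 | 0.0774 | 0.0769 | 0.0809 | +0.7% | −4.4% |
| 1.1 | 0.0867 | 0.0850 | 0.0867 | +2.0% | 0.0% |

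Against residual noise, the excess is 0.35–1.1% at 7.6% missing and 0.15–0.44% at 3% missing.

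**Simulation.** 335 per arm, 51 missing per arm, 50 imputations, observed mean change −0.4, strata omitted, 4,000 runs per setting, true difference 0.

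| Week 26 SD, ρ | SE, SAP noise | SE, residual noise | SE, SD-of-change noise | Empirical SE |
|---|---|---|---|---|
| 0.95, 0.22 | 0.0801 | 0.0796 | 0.0835 | 0.069 |
| 1.1, 0.36 | 0.0882 | 0.0865 | 0.0882 | 0.075 |

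The SEs are a little above the closed form because imputed patients also differ from observed patients in mean change and baseline slope. The point estimate is the same to four decimals under all three noise rules.

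- CI half-width, SAP against residual noise: 0.157 vs 0.156, and 0.173 vs 0.170.
- Probability of meeting the 0.3 margin: 98.1% vs 98.2%, and 95.2% vs 95.6%. Against 0.4 it exceeds 99.9% throughout.
- Excess of the mean SE over the empirical SE that remains with residual noise: (0.0796 − 0.069)/(0.0801 − 0.069) = 95%, and (0.0865 − 0.075)/(0.0882 − 0.075) = 87%.

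**True difference of 0.40.** Returning both arms to baseline shrinks the contrast to about 0.40 × (1 − 0.152) = 0.34, whichever noise is used. Noninferiority at 0.4 was then declared in:
- 7.8% (SAP) vs 8.1% (residual) at ρ 0.22;
- 6.3% vs 6.8% at ρ 0.36;
- 9.2% vs 12.0% at ρ 0.6 with Week 26 SD 0.95.

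Monte Carlo error is about 0.4 to 0.5 points. If washout is accepted as the estimand's assumption, these are not type I errors. If it is not, the wider noise partly offsets the shrinkage.

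**The case for a change.** The strongest case for a change is that this is a primary analysis at full alpha, the mechanism is plain in the text, and a remedy costs one sentence. The fallback is also not remote, since the third SAP version added it for a thin reference group.

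The effect grows with the correlation. At ρ = 0.6 and 15.2% missing, simulated SEs are 0.0689 vs 0.0644 (Week 26 SD 0.95) and 0.0793 vs 0.0741 (SD 1.1), an excess of about 7%. For an assumed true difference of −0.2 tested at the full 0.05, H4 power would fall by 4.8 to 6.6 points. At that correlation the SAP rule also exceeds SD-of-change noise, and more of the over-width would be removed by residual noise.

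The algebra stands and so does the dependence on ρ. But ρ = 0.6 implies an SD of change of √(0.64 + 0.9025 − 0.912) = 0.79, or √(0.64 + 1.21 − 1.056) = 0.89, both well below the planning 1.1. On the planning SD the H4 loss is 0.5 to 1.9 points under the same assumptions. The alpha that actually reaches H4 depends on weights in a figure not reproduced here.

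The 15.2% is a planning allowance and caps nothing. Continued follow-up after stopping IP could lower it and heavier dropout could raise it; at 20% missing the excess is 0.8–2.5%.

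**Conclusion.** No change to the plan. The noise variance exceeds the ANCOVA residual variance, but that does not make it wrong. Under washout an imputed patient's change from baseline is the noise itself, so the SD of change is at least as natural a target. The SAP noise exceeds that SD only if ρ > s_b/(2 s_w), which is 0.42 or 0.36 for the assumed SDs; on the planning SD it is below or equal to it. Neither benchmark is identified for patients off IP whose Week 26 value is missing.

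The gain from residual noise would be small: 0.7–2.0% of the SE, or 0.001 to 0.003 in half-width, only if the fallback is used and only for the ITT estimand. It would leave about 87–95% of the over-width and make the noninferiority test slightly less conservative. Only the rule could be fixed before unblinding, since its value needs treatment codes.

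That the noise adds no bias is true of its variance alone. The shrinkage towards equality comes from the washout assumption and is a separate matter. These sizes rest on the assumed baseline and Week 26 SDs, Rubin's rules and 15.2% missing. A baseline-to-Week 26 correlation well above what the planning SD implies would enlarge them.
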